Principal Investigator: [name], MPH

Study Purpose and Rationale:

Hydromorphone is a commonly prescribed opioid analgesic that is used in both adults and children. It can be administered by the oral (PO) route, but is associated with poor bioavailability and slow time to onset of action. It can also be administered by the intramuscular (IM) or intravenous (IV) routes, but both require needle sticks, which children report to be their most feared medical procedure, and that which they find highly distressing. The intranasal (IN) route is a safe and effective way of administering opioid analgesics (e.g. fentanyl, sufentanil) in both adults and children. Although there have been studies evaluating the bioavailability, pharmacokinetics, clinical efficacy, and adverse events of IN hydromorphone in adults, IN hydromorphone has not been yet been studied in children. Given the safe and efficacious reports of IN hydromorphone in adults, and the potential benefits of administering hydromorphone by the IN route for children, we aim to conduct a pilot study to evaluate the efficacy of IN hydromorphone in reducing pain in children with acute pain who present to the pediatric emergency department.

Study Design:

This will be a pilot study, in which we will prospectively enroll a convenience sample of children who present with moderate to severe acute pain to the pediatric emergency department of a single institution.

Study Procedures:

The treating physician will determine if their patient fulfills inclusion criteria. If they do, the physician will approach the patient and family to see if they are willing to discuss the study with a member of the study team. If they agree, a member of the study team will determine if the patient is eligible for the study, and if they are, they will then approach the patient and family to discuss the study and obtain consent. The consent and assent process will be conducted in the patients primary language (English or Spanish only). Patients who are eligible for the study and have provided consent/assent will first have their pain intensity measured within 15 minutes prior to receiving the IN hydromorphone (baseline assessment). They will be monitored as per standard practice by the health care providers in the emergency department for patients receiving an opioid analgesic (i.e. pulse oximetry, interval vital signs including blood pressure). All pain assessments will be performed using the Faces Pain Scale – Revised (FPS-R) and verbal Numeric Rating Scale (vNRS) by a research assistant, coordinator or study team physician. A nurse will administer the IN hydromorphone using a mucosal atomization device: this is Time 0. Immediately after the medication is administered, the patient will be asked to report how much pain or discomfort they experienced with the administration (also using the FPS-R and vNRS). The patient will have their pain assessed at the following time points: 5 minutes, 15 minutes, 30 minutes, 45 minutes, 60 minutes, and then every 30 minutes thereafter until 6 hours, the patient is discharged from the emergency department, or a non-IN hydromorphone rescue analgesic is administered (see following paragraph regarding first and second rescue medication assessments at 15- and 30-minutes). This non-IN hydromorphone rescue analgesic will be considered after 60 minutes, and its administration will be determined at the discretion of the primary attending physician. If a non-IN hydromorphone rescue analgesic is administered, the time when it

was given will be recorded. The attending physician may administer an analgesic of their choice as a rescue analgesic (e.g. IV hydromorphone, IV morphine) as per standard practice.

At the 15- and 30-minute marks, the patient will undergo a first and second rescue IN hydromorphone assessment. They will be asked if their pain is, "much less, a little less, the same, or worse" compared to before they received the IN hydromorphone. If they reply, "the same", or "worse", they will receive an additional rescue dose of IN hydromorphone at 0.015 mg/kg, maximum single dose of 2 mg. We will also ask the patient, " "Do you want more medicine to make your pain less?", as patients who report that their pain is "a little less" or "a lot less" may still not have achieved adequate pain relief, and this deficit will not be identified without asking this specific follow-up question to confirm adequacy of pain relief. Intranasal hydromorphone has been shown to reliably produce adequate analgesia by 10 minutes when an adequate dose has been administered. Therefore, determining whether additional analgesia is required at 15 minutes is a reasonable amount of time to wait after administering a dose of IN hydromorphone to see if a patient experienced any improvement in pain intensity. This methodology has been used in prior pilot studies of analgesics, to prevent patients from receiving inadequate analgesia if the initially selected dose was not sufficient, and so that an effective dose can be determined. In addition, administering additional reduced doses (i.e. half initial dose) after 15 minutes of receiving a dose of parenteral opioid analgesic, if there has been no improvement in pain intensity, is standard practice when administering IV opioid analgesics as part of typical clinical care when treating pain in children.

Adverse events will be assessed and recorded by the research assistant or study investigator, in conjunction with the nursing staff and treating physician. These adverse events will include those considered minor and major. The specific adverse events being assessed are detailed on pages 8 and 9 of the data collection form. All adverse events will be assessed every hour.

Patients will receive IN hydromorphone (2 mg/mL concentration) at a dose of 0.03 mg/kg, maximum single dose 4 mg. This dose was obtained from prior studies demonstrating that the bioavailability of IN hydromorphone was 55%, and clinical studies showing that at least 4 mg was required to achieve clinically meaningful improvement in pain in adults, with no incidence of serious adverse events, and no significant difference in adverse events compared to lower doses. The usual pediatric dosing of IV hydromorphone is 0.015 mg/kg, so the use of 0.03 mg/kg is consistent with this demonstrated bioavailability of IN hydromorphone. In addition, other commonly-used IN analgesics and sedatives (e.g. fentanyl, midazolam, ketamine) are dosed in a similar fashion: that is, at least double (and for some medications, up to five times) the IV dose is used when administering the medication by the IN route. This dosing strategy and interpretation of the bioavailability and pharmacokinetic data for intranasal hydromorphone was discussed with [name] (Director of Biomarkers Core Laboratory of the Irving Institute for Clinical and Translational Research).

Statistical Procedures:

We will use descriptive statistics (mean/SD, median/IQR) to describe our patient population and their characteristics. Our primary outcome of median change in pain intensity will be measured using the Faces Pain Scale – Revised (FPS-R), a validated pain scale in children ages 4 to 17 years old, which allows a child to report their pain intensity on a scale from 0 (no pain) to 10 (most pain). Median change in pain intensity will also be measured using the verbal Numeric Rating Scale (vNRS), which assesses pain by asking how much pain they have on a scale from 0 to 10. We will report the median 16Mar2018

change in pain intensity of our patients who receive intranasal hydromorphone. Our secondary outcome of adverse events will be reported using descriptive statistics, i.e. the proportion of patients who experienced each type of adverse events. We will also be recording the time at which rescue analgesics are administered, and report the results as a Kaplan-Meier curve. For the purposes of this pilot study, we will enrol 40 patients, which has been previously demonstrated to be sufficient in similar pilot studies evaluating the analgesic efficacy of other medications.

Potential Risks:

The risks associated with receiving intranasal hydromorphone are the same as if administered by another route (e.g. intravenous). There is a chance that the patient may not experience the same degree of pain relief that they may have experienced if they had received intravenous hydromorphone. However, patients will have their pain assessed as per usual standard care, and can receive additional required analgesics at any point in time if their pain relief is inadequate. The procedures involved in this study do not increase the risk for adverse events normally associated with receiving hydromorphone. Potential Benefits: Provide information regarding any anticipated benefits of participating in this research. There should be a rational description of why such benefits are expected based on current knowledge. If there is unlikely to be direct benefit to participants/subjects, describe benefits to society. Please note that elements of participation such as compensation, access to medical care, receiving study results, etc. are not considered benefits of Risks, Benefits & Monitoring THe most common adverse events reported by patients who have received intranasal hydromorphone include bad taste in mouth (21%), dizziness (14%), somnolence (15%), nausea (6%), and vomiting (2%). Except for bad taste in mouth, the incidence of these adverse events associated with intranasal hydromorphone were all less than that experienced by patients who received the same dose of intravenous hydromorphone (Coda et al. 2003)

Potential Benefits:

If the treating physician was going to initiate an intravenous line for the sole purpose of administering a parenteral opioid analgesic to treat the child's pain, one potential benefit is that receiving intranasal hydromorphone instead would spare the child a painful and distressing needle stick. Another benefit is that the patient may receive longer duration of analgesia than if they had received intranasal fentanyl, which is a commonly-administered parenteral opioid analgesic in the pediatric emergency department.

Alternatives:

An alternative to participation in this study is to choose not to participate, or to receive an opioid analgesic by an alternate route (e.g. oral, intramuscular, or intravenous).

Data and Safety Monitoring:

Data will be reviewed on an ongoing basis by the PI with each patient enrolled. On an ongoing basis, the investigators will monitor accrual of study subjects, assess adherence to study protocol, assess 16Mar2018 Page 3 of 4

data quality, and collect and review adverse events and other subject safety matters. We will submit to the IRB protocol deviations and any requested protocol modifications. A data safety monitoring board (DSMB) consisting of two physicians unrelated to the study will be formed to evaluate safety and adherence to the protocol (Drs. [name] and [name], Division of Pediatric Emergency Medicine). The first review will be conducted after the first 10 patients are enrolled, and then the DSMB will convene every 6 months until the study is completed.

Adverse Event Reporting: An adverse event is any untoward medical occurrence by a subject. For each patient, the investigators will evaluate adverse events after completion of enrollment. All unanticipated problems (i.e. unexpected events, outcomes, or occurrences, at least possibly related to the research, and suggest an increase in risk of harm to subjects or others) will be reported to the IRB. This reporting will be done promptly, but no later than one week after the occurrence or after the PI acquiring knowledge of the unanticipated problem, and will also be reported at time of continuing review. All data will be maintained on password-protected computers and in locked file cabinets in a locked room to which only authorized study personnel will have access. Only approved research staff will view the clinical information of children enrolled in this study. We will retain study records and documentation for 3 years after the last enrolled patient has completed all study procedures.

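### The baseline pain score may be up to 15 minutes old at dosing, so pain change in that gap, in either direction, enters the uncontrolled primary change score

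*Combined protocol and SAP*

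**What the plan says.** All of the following is in the combined protocol and SAP.

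- **Baseline (Study Procedures).** Patients "will first have their pain intensity measured within 15 minutes prior to receiving the IN hydromorphone (baseline assessment". No other pre-dose pain score is described.
- **Dosing (Study Procedures).** "A nurse will administer the IN hydromorphone using a mucosal atomization device: this is Time 0".
- **Contact right after the dose (Study Procedures).** "Immediately after the medication is administered, the patient will be asked to report how much pain or discomfort they experienced with the administration". The same two scales are used, but for discomfort from the spray and not for the presenting pain.
- **Who scores (Study Procedures).** Pain is assessed "by a research assistant, coordinator or study team physician".
- **Post-dose scores (Study Procedures).** These are due at "5 minutes, 15 minutes, 30 minutes, 45 minutes, 60 minutes, and then every 30 minutes thereafter until 6 hours", ending earlier on discharge or when a rescue analgesic other than IN hydromorphone is given.
- **Rescue assessments (Study Procedures).** "At the 15- and 30-minute marks, the patient will undergo a first and second rescue IN hydromorphone assessment". The child is asked to judge pain "compared to before they received the IN hydromorphone".
- **Primary outcome (Statistical Procedures).** The outcome is the median FPS-R change, with vNRS reported alongside. Neither the time point nor the reference score is stated.
- **Design (Study Design).** This is a single-institution pilot with no control arm described. The sample size of 40 rests on precedent.

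**The concern.** A change from baseline contains everything that happens between the two scores. With a concurrent control arm, pain drift before dosing would be expected to affect both arms alike. Here there is nothing to set it against, so whatever happens between the baseline score and Time 0 becomes part of the reported change. Positioning, ice or reassurance may lower acute pain in those minutes; movement or examination may raise it.

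The window is also long on the protocol's own clock. The protocol argues that "Intranasal hydromorphone has been shown to reliably produce adequate analgesia by 10 minutes" if the dose is adequate. A baseline that may be 15 minutes old can therefore be older than the time in which the drug is expected to act. The scores most exposed are the earliest ones. These are also the scores that reflect the first dose alone, because repeat IN doses are possible from 15 minutes.

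At stake is the size of the change that the pilot reports, not its direction of treatment or anyone's care.

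**Working it through.** The plan has no figure of its own to reproduce here. It gives no SD, effect size, alpha or power, and this point does not depend on the sample size.

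**Inputs from the documents.** Baseline window W = 0 to 15 minutes; post-dose scores at t = 5, 15, 30, 45 and 60 minutes and later; first rescue assessment at 15 minutes; n = 40.

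**Inputs assumed.** Drift d = 0.5 to 1 point per 15 minutes, all in one direction; SD of the change score 2 to 3 points. The documents give neither.

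**Step 1: window against follow-up.** The ratio is 15/t. The largest share of the baseline-to-score time that precedes the drug is 15/(15 + t).

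| Score at | 15/t | Largest pre-dose share |
|---|---|---|
| 5 min | 3.0 | 15/20 = 75% |
| 15 min | 1.0 | 15/30 = 50% |
| 30 min | 0.5 | 15/45 = 33% |
| 45 min | 0.33 | 15/60 = 25% |
| 60 min | 0.25 | 15/75 = 20% |

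These are shares of elapsed time, not of the change score.

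**Step 2: shift in the median.** With linear drift, a child scored L minutes before dosing carries d × L/15 points into the change.

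- Every baseline 15 minutes early: d × 15/15 = 0.5 to 1.0 points. This is the ceiling.
- Lags spread evenly over 0 to 15 minutes (mean 7.5): d × 7.5/15 = 0.25 to 0.5 points.
- Window cut to 5 minutes, lags spread evenly (mean 2.5): d × 2.5/15 = about 0.08 to 0.17 points.
- Score taken immediately before dosing: 0.

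A simulation with normal change scores (SD 2.5 assumed) gave matching shifts in the median: 0.5 and 1.0; 0.25 and 0.5; 0.09 and 0.17; and 0. The shift is positive when pain eases before dosing and negative when it rises.

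**Step 3: scale.** The approximate 95% half-width of a median at n = 40 is 1.96 × 1.2533 × SD/√40. For SD 2 this is 0.78, and for SD 3 it is 1.17, so about 0.8 to 1.2 points. With evenly spread lags the assumed bias is smaller than this. Unlike sampling error, it would not shrink with more patients.

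**The case against.** The strongest reply is that 15 minutes is a ceiling. Consent, baseline and dose follow one another, and actual lags may be short. Drift may differ in direction from child to child and partly cancel in a median. The study is a descriptive pilot of 40, and natural change after dosing is just as uncontrolled and runs for up to 6 hours. A Time 0 baseline removes at most 15 minutes of it. All of this stands and limits the size of the point. It does not give a reason to prefer the wider window, and the pre-dose part is the part that can be removed.

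Several stronger readings are tempting but not supported:

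- *That a child whose pain eased before dosing is counted as a responder.* The plan defines no responder and plans no responder analysis. Such a child is credited with improvement in a median change, no more.
- *That the bias favours the drug.* Rising pain before dosing works the other way, and the documents do not show which prevails.
- *That the window merely matches the first response interval.* The first post-dose score is at 5 minutes; 15 minutes matches only the first rescue assessment.
- *That the 5-minute score is the best reading of response.* It comes before the protocol's own 10-minute point for adequate analgesia.
- *That the rescue question conflicts with the baseline.* It asks for the child's own recollection, and no planned analysis ties the answer to the recorded score. An older baseline does not alter the rescue decision.
- *That nothing confirms the child's pain level, or its timing, at dosing.* The inclusion criteria and the data collection form to which the protocol refers are not in the available text, so this cannot be judged.

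**Conclusion.** The point holds as a modest, avoidable measurement weakness. The only planned pre-dose score may be up to 15 minutes old at Time 0, and any change in that gap goes into the primary result. Under one-directional drift of 0.5 to 1 point per 15 minutes, the bias is about 0.25 to 0.5 points with evenly spread lags and 0.5 to 1.0 at most.

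The conclusion rests on three things. First, change is taken from the score labelled baseline; this is the natural reading, since no other pre-dose score is planned, but it is not stated. Second, the drift size is assumed. Third, the actual lags are unknown. Its weight also turns on the primary time point, which the plan leaves open: it matters most at 5 and 15 minutes and much less at 60.

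**What to change.** In Study Procedures, have the study staff member take FPS-R and vNRS immediately before atomisation and record the clock time. In Statistical Procedures, name that score as the baseline for all change scores. If an earlier score is taken when the child is assessed for the study, keep it for eligibility only.

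The cost is about one sentence in each section and under a minute at the bedside. Study staff already have to use the same scales with the child straight after the dose, so no extra people, visits or instruments should be needed. Treatment and the sample size of 40 are unchanged. Some baselines may come out slightly lower than under the wider window. Naming the primary time point as well would show how much early drift could have mattered.

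### The protocol describes no pre-dose symptom check and no new-or-worse condition for adverse events, so symptoms already present before dosing may be counted in the secondary outcome

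*Combined protocol and SAP*

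**What the plan says.** All references are to the combined protocol and SAP.

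- **Baseline (Study Procedures).** Consented children "will first have their pain intensity measured within 15 minutes prior to receiving the IN hydromorphone (baseline assessment". Pain is the only item named for that assessment. The other monitoring mentioned is usual emergency department practice "for patients receiving an opioid analgesic (i.e. pulse oximetry, interval vital signs including blood pressure").
- **Adverse-event schedule (Study Procedures).** "All adverse events will be assessed every hour". No start time is given and no pre-dose assessment is mentioned. The research assistant or a study investigator records events together with nursing staff and the treating physician.
- **Event list (Study Procedures).** "The specific adverse events being assessed are detailed on pages 8 and 9 of the data collection form". That form is not part of the documents.
- **Definition (Adverse Event Reporting).** "An adverse event is any untoward medical occurrence by a subject". It does not require onset or worsening after dosing, or a causal link. The same section adds: "For each patient, the investigators will evaluate adverse events after completion of enrollment".
- **Analysis (Statistical Procedures).** Adverse events are the one outcome labelled secondary, summarised as "the proportion of patients who experienced each type of adverse events". No rule is given for symptoms that predate the dose.
- **Design (Study Design).** One treated convenience sample; no comparator is described.

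**The concern.** The two labelled outcomes are handled differently. Pain is analysed as change, so each child's pre-dose value is part of the outcome. Adverse events have no described pre-dose value, although the same need arises. These children arrive with moderate to severe acute pain, and some could plausibly be nauseated, vomiting, dizzy or drowsy from their condition or from earlier medicine. With no control group, a child's own pre-dose status is the only reference within the study for telling a symptom of the presenting condition from one that began after the drug.

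The protocol's rationale says the intranasal route for this drug has not been studied in children, so these proportions would contribute to a first paediatric safety description. The safety board first looks after 10 children, when one pre-existing symptom counted as an event moves a rate by 1/10, or 10 percentage points. Symptom status that was not recorded before Time 0 cannot be reliably recovered at analysis.

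**Working it through.** **Is there a plan figure to reproduce?** No. The sample size of 40 is justified by precedent only, with no inputs, and no target adverse-event rate is stated. The question is what is recorded and what is counted.

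**Step 1: follow a pre-existing symptom through the plan.** Take a child who is nauseated on arrival and still nauseated at the first hourly check.

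1. At the baseline contact, the protocol describes a pain score only, so no nausea entry is described.
2. Pulse oximetry and vital signs do not capture nausea, vomiting or dizziness, and are not a sleepiness assessment.
3. At the hourly check, nausea is present and meets the all-cause definition.
4. In the analysis, the child is in the numerator for nausea unless someone has removed the event. The plan gives no rule for doing so.

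The documents say neither that such a symptom is counted nor that it is excluded.

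**Step 2: how sensitive is the reported proportion?**

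Inputs:
- *p*, the rate of new events. For illustration, the intranasal rates quoted under Potential Risks: nausea 6%, vomiting 2%, dizziness 14%, somnolence 15%. They are attributed there to a source whose title describes healthy volunteers.
- *b*, the proportion with the symptom before dosing. **This is an assumption**; the documents give no figure. Range used: 0% to 30%.
- *n* = 40 (Statistical Procedures).

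Further assumptions: *b* and *p* are independent, and every pre-dose symptom persists to a post-dose check and is recorded as an event.

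Formula: crude proportion = 1 − (1 − *b*)(1 − *p*).

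For nausea, *p* = 0.06:
- *b* = 0: 1 − 1.00 × 0.94 = 6.0%, or 2.4 of 40
- *b* = 0.05: 1 − 0.95 × 0.94 = 10.7%, or 4.3 of 40
- *b* = 0.10: 1 − 0.90 × 0.94 = 15.4%, or 6.2 of 40
- *b* = 0.20: 1 − 0.80 × 0.94 = 24.8%, or 9.9 of 40
- *b* = 0.30: 1 − 0.70 × 0.94 = 34.2%, or 13.7 of 40

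The same formula for all four symptoms:

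| Symptom | b = 0% | 5% | 10% | 20% | 30% |
|---|---|---|---|---|---|
| Nausea | 6.0% | 10.7% | 15.4% | 24.8% | 34.2% |
| Vomiting | 2.0% | 6.9% | 11.8% | 21.6% | 31.4% |
| Dizziness | 14.0% | 18.3% | 22.6% | 31.2% | 39.8% |
| Somnolence | 15.0% | 19.3% | 23.5% | 32.0% | 40.5% |

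The relative effect is largest where the new-event rate is lowest. At *b* = 10%, nausea is multiplied by 15.4/6 = 2.6 but dizziness by only 22.6/14 = 1.6. At *b* = 0 nothing changes.

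**Step 3: set this against sampling error.** Exact (Clopper-Pearson) 95% intervals with 40 children: 2/40 (5%) gives 0.6% to 16.9%; 6/40 (15%) gives 5.7% to 29.8%. These counts are close to the nausea results at *b* = 0 and *b* = 10%, and the intervals overlap widely. A shift of that size would be hard to see in the data, and a larger sample would not remove it.

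**The case against.** The strongest reply has five parts.

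- **The deciding form is unseen.** The event items are on a data collection form that was not supplied and may hold a baseline entry. The hourly schedule has no stated start, so a pre-dose entry is not excluded. This stands: the protocol describes no pre-dose check, but a reader should not infer that none is made. Even if the form has such an item, Statistical Procedures does not say how it would be used.
- **The definition is all-cause.** A count of any untoward occurrence is not biased against its own definition, and over-counting is the cautious direction for safety. This is fair, and the plan does not claim that every event is due to the drug. An all-cause count in one arm still says little about what the drug adds.
- **Clinicians are involved.** The treating physician has seen the child before dosing and takes part in recording, and investigators evaluate each patient's events. Some pre-existing symptoms may well be screened out, so it cannot be said that they will be counted. Without a written rule and a recorded baseline, however, such screening can be neither reproduced nor audited.
- **The size is assumed.** No prevalence is given, persistence is not established, and bad taste, the most frequent quoted event at 21%, is not one of the symptoms at issue. This stands in full.
- **No stated decision depends on these rates.** There is no test, event threshold or rate-based stopping rule. No comparison with the rates under Potential Risks is planned, and a baseline check would not make it a fair one: that source is a single-dose study in healthy volunteers, whereas this trial allows repeat doses in children in pain. This also stands, and it limits the consequence to how the safety results are described.

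**Conclusion.** The concern holds as a gap in ascertainment and outcome definition. As written, symptoms present before Time 0 may be included in the adverse-event proportions, and they could not be reliably separated from new events unless the data collection form records pre-dose status.

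The size is unknown. The calculated range for nausea, from no inflation at 0% prevalence to 34.2% at 30%, shows sensitivity under assumed prevalence, independence, full persistence and full counting. A reader might infer that the reported safety rates will be overstated several-fold. The documents do not support that, since they give no pre-dose prevalence and do not say that such symptoms are counted. The primary pain outcome is not affected. The change is worth making before enrolment because the missing information can only be collected prospectively.

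**What to change.** 1. **Study Procedures:** state that the existing adverse-event checklist is completed once at the pre-dose baseline contact, with enough detail on severity for later worsening to be recognised. If the form already does this, say so.
2. **Statistical Procedures:** define the secondary outcome as the proportion of patients with each event type that is new or worse than baseline. List symptoms present at baseline separately, so that the all-cause picture remains visible.

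The cost is a few lines of protocol text, possibly one added entry on an existing form, and about a minute per child at a contact that is already scheduled. Reported rates will be lower wherever symptoms were present before dosing and did not worsen; the separate baseline listing makes that transparent. No treatment or monitoring rule changes.

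### No pain score is taken just before non-IN rescue, so after 60 minutes the last score on IN hydromorphone can be almost 30 minutes old and may miss the pain that led to rescue

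*Combined protocol and SAP*

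**What the plan says.** Study Procedures sets the post-dose pain scores at "5 minutes, 15 minutes, 30 minutes, 45 minutes, 60 minutes, and then every 30 minutes thereafter". The last stretch of the schedule, with the three things that end it, is set out as "every 30 minutes thereafter until 6 hours, the patient is discharged from the emergency department, or a non-IN hydromorphone rescue analgesic is administered".

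On when that rescue may happen, the same section says "This non-IN hydromorphone rescue analgesic will be considered after 60 minutes" and that "its administration will be determined at the discretion of the primary attending physician". Potential Risks is wider: patients "can receive additional required analgesics at any point in time if their pain relief is inadequate".

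On what is captured at that moment, Study Procedures names one item: "If a non-IN hydromorphone rescue analgesic is administered, the time when it" was given. It requires no FPS-R or vNRS score there. The rescue assessments at 15 and 30 minutes in the same section decide on further IN hydromorphone only, so they do not supply one.

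Statistical Procedures makes the median change in pain on the FPS-R the primary outcome, with the vNRS alongside, and plans a Kaplan-Meier curve of rescue times. It gives no time point for the change, and no rule for children whose scoring has ended.

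**The concern.** Scoring becomes sparser at the same point that non-IN rescue becomes available. A child can be comfortable at one scheduled score, be in marked pain 20 minutes later, receive another analgesic and leave the series. The study would then hold the earlier, better score and a clock time.

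The possible loss is not random. According to Potential Risks, extra analgesia is for inadequate relief, so pain just before rescue will tend to be worse than at the preceding score. With a single arm, no comparison group offsets this. What is at stake is the later part of the pain curve and any statement about how long relief lasts. The protocol itself raises duration under Potential Benefits, where it suggests longer relief than IN fentanyl might give.

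This is a matter of data collection. An analysis rule can be written later, but a score not taken before another analgesic cannot be recovered, because later scores would reflect that drug as well.

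**Working it through.** The plan gives no figure of its own to reproduce here. The only design number is the sample of 40, set by precedent, and the point does not depend on it.

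**Inputs (Study Procedures)**
- Scheduled times: 0 (dose; the baseline score is taken shortly before), 5, 15, 30, 45 and 60 minutes, then 90 to 360 by 30.
- Post-dose scores: 5 up to 60 minutes, plus (360 − 60)/30 = 10 afterwards, so 15 in all.
- Planned start of non-IN rescue: after 60 minutes, with no link to a scheduled score.

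**Age of the last score**

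Age at rescue = rescue time − latest scheduled time not after it. Its upper limit is the gap between neighbouring scheduled times.

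| Period | Gaps (min) | Age of last score at rescue |
|---|---|---|
| 0 to 60 min | 5, 10, 15, 15, 15 | 0 to just under 15 min |
| 60 to 360 min | 30 throughout | 0 to just under 30 min |

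**Typical age after 60 minutes.** The documents give no distribution of rescue times. If they are uniform within each 30-minute interval (assumption):
- mean age = 30/2 = 15 minutes;
- share older than 15 minutes = (30 − 15)/30 = 50%;
- share older than 10 minutes = (30 − 10)/30 = 67%.

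A simulation of 400,000 uniform rescue times between 60 and 360 minutes gave a mean of 15.0 minutes and shares of 50% and 67%. If rescues cluster just after a poor scheduled score, the ages are shorter.

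**Constructed illustration (not trial data).** Baseline 8, score 4 at 60 minutes, pain back to 8, non-IN rescue at 85 minutes:
- age of last score = 85 − 60 = 25 minutes;
- recorded last change = 4 − 8 = −4;
- change at rescue = 8 − 8 = 0.

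**Why no bias figure follows.** The effect on a reported median depends on the proportion rescued, the rescue times, how far pain rises between the last score and rescue, and the time point and rule for the change. The documents give none of these.

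**With the fix.** A score immediately before rescue brings the age to about 0 minutes, against a current maximum of just under 30.

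**The case against.** The strongest reply is that no planned analysis uses the last score. Statistical Procedures promises a median change and nothing about the last observation or carrying scores forward. If the change is taken at 15, 30 or 60 minutes, it is largely untouched. At 90 minutes or later, the distortion comes mainly from stopped children dropping out of the summary, and an off-schedule score would not enter that summary without an added rule. This stands. A reader might infer that the primary result is biased towards benefit, but the documents show only that later or last-score summaries could be. It also means that the fix needs an analysis rule as well as a measurement.

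A reader might also infer that every rescued child lacks the relevant score, and turn an assumed 10–30% rescue rate into 0.10 × 40 = 4 to 0.30 × 40 = 12 children. That does not follow. A rescue given straight after a scheduled score is already covered, and no rescue rate is stated.

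Nor is the Kaplan-Meier curve impaired. It uses the rescue time, which is recorded, and such a curve does not display pain intensity in any case.

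Extending the argument to discharge is also tempting, since discharge ends scoring too and the age limit is the same. But discharge without rescue does not signal failed relief, so the documents give no direction for any error there.

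Finally, the data collection form cited in Study Procedures was not available, and it may hold a pain field beside the rescue time. The protocol text does not require one, though. The mention under Potential Risks of pain assessment in usual care does not schedule an FPS-R or vNRS score at rescue.

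What survives is the gap itself, and the fact that it cannot be repaired afterwards.

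**Conclusion.** The point holds as a limited, inexpensive improvement to measurement. After 60 minutes the last study score before non-IN rescue is 0 to just under 30 minutes old. That range follows from the schedule alone. The 15-minute average needs the uniform assumption. The missed scores would tend to be the worse ones, provided rescue is given for inadequate relief as Potential Risks describes. The likely direction is therefore towards too favourable a picture in summaries after 60 minutes and in any summary of the last score on IN hydromorphone. The amount cannot be calculated from the documents.

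If rescue is given within the first 60 minutes, which the Potential Risks wording would permit, the limit is just under 15 minutes. The two statements on when additional analgesics may be given should be reconciled, since they determine which limit applies.

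**What to change.** In Study Procedures, require one FPS-R and vNRS score immediately before any non-IN rescue analgesic, stating that rescue is not to be delayed for it. Check that the data collection form has a field for it next to the rescue time.

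In Statistical Procedures, state that the pre-rescue score is reported alongside each rescue time, and that it serves as the child's last score on IN hydromorphone in summaries at times after rescue. Without that sentence the extra score would have no defined role.

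The cost is at most one extra pair of scores per rescued child, taken by study staff already doing the follow-up assessments. The pair will occasionally be missed when rescue is urgent, and this should be recorded as missing. The change affects no dose, rescue criterion or treatment decision.

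A score at discharge could be added in the same way, but it is optional.
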